10.2.4 Randomization Procedures

An independent statistician will develop a randomization list using SAS. Randomization in permuted blocks will be used to achieve balance across treatment groups. The randomization scheme consists of a sequence of blocks such that each block contains a pre-specified number of treatment assignments in random order. The purpose of this is to balance the randomization scheme at the completion of each block. The target sample size is 360 evaluable subjects.

10.2.5 Analyses of Safety

All adverse events and serious adverse events will be coded using the Medical Dictionary for Regulatory Activities Version 12.0, which is a registered trademark of the International Federation of Pharmaceutical Manufacturers and Associations. The number and percentage of subjects reporting at least one occurrence of an adverse event and/or serious adverse event for each system organ class and preferred term will be tabulated. Term will also be tabulated by severity and by the relationship to the procedure. For multiple occurrences of the same adverse event with different severities, the adverse event with the highest severity will be tabulated. For multiple occurrences of the same adverse event with different relationships to the procedure (related and not related); the adverse event will be tabulated as related. All adverse events and or serious adverse events for all subjects will be presented in data listings. Narratives will also be prepared for each serious adverse event.

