- Women of childbearing potential will undergo urine pregnancy testing (Qualitative HCG) to confirm absence of pregnancy at the day 1 of treatment clinic visit prior to administration of study drug.
- A diary completed by subject will be collected before FMT and on follow up days 7(+3), 14(+3) 30(+10), 60(+10), 90(+10) and 180(+20) days after FMT treatment. Subjects may submit diaries with stool samples at the University of Texas School of Public Health, or may fax, email, or mail to the study site. For diary copies received in email or fax, an attempt will be made to obtain the originals from subjects to be taken to the study site subsequently. Diaries serve as tools for subjects to record daily bowel movements and weekly weight. Subjects will be recommended to measure weight at home each Sunday morning before eating and record on follow up diaries providing they have a scale or balance. If they do not have the means to measure their weight this is not a protocol deviation. Additionally, the pre-treatment diary will include daily record of solicited symptoms from day of enrollment until a day before treatment Day 1 (prior to bowel prep) to establish baseline patterns should an adverse event occur in the future. Solicited symptoms include diarrhea, nausea, vomiting, gas/flatulence, abdominal distension, abdominal cramps/pain, constipation, rectal bleeding,

fatigue/malaise, chills/shivering and fever (>99.9 F). The diaries on follow up days 7 and 180 will include a brief survey to assess subject-reported experience of FMT treatment. Diaries that are received out of the window or missed diaries are not a protocol deviation.

Study assessments and procedures will include the following:

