9.1.4 Unexpected adverse event:

An adverse event or suspected adverse reaction is considered 'unexpected' if it is not described in the general investigational plan or is not listed at the specificity or severity that has been observed.

9.1.5 Adverse events of special interest (weight gain, new or worsening autoimmune conditions, and metabolic syndrome):

Adverse events of special interest such as new or worsening autoimmune conditions and metabolic syndrome will be asked from subjects during follow up phone visits. Subjects will be asked at the enrollment visit that how much they weighed before the first CDI episode to take into consideration any weight loss resulting from CDI bouts. To obtain baseline data, subjects will be weighed on treatment day 1 clinic visit prior to administration of FMT treatment. After FMT treatment, subjects will be recommended to measure weight at home each Sunday morning before eating and record on follow up diaries, providing they have a scale or balance.

To account for normal weight fluctuations, subject-reported weekly weight data from diaries will be assessed for AE (>5% change from baseline weight) at days 60 and 180 phone visits.

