10.2.3 Analysis Populations

Two primary analyses will be performed:

- 1) Analysis for safety and efficacy between three groups (1-3) receiving varied doses of lyophilized product generated from stool (50g for both treatment days; 100g on the first treatment day and 50g on the second treatment; 100g for both treatment days)
- 2) Analysis for safety and efficacy between two groups (3 and 4) with and without bowel preparation and Imodium receiving same high doses of lyophilized product (100g for both treatment days).

- All analyses will be conducted using the intent-to-treat population. Intent-to-treat is defined as all subjects who have started the procedure.
- Listings and summary tables with descriptive statistics will be prepared for demographic data (gender, date of birth, race/ethnicity), and medical history data.

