13. CONTACTS ABOUT STUDY

For study details, the study coordinators at Kelsey Research Foundation [REDACTED] |

For product related issues - [name] [REDACTED]

For subjects at Kelsey-Seybold Clinic - [name] [REDACTED]

For University of Texas/Memorial Hermann Hospital - [name] [REDACTED] The
University of Texas Health Science Center Committee for the Protection of Human Subjects
[REDACTED].

Kelsey Seybold Clinic Review Committee at [REDACTED]

TABLE 1: STUDY SCHEDULE:

Assessment and Procedures	Enrollment (day -14 to -1)	Treatment Days		Follow Up and Safety Assessment Period via Telephone							Un scheduled Visit	Early Termination Visit
		Day 1	Day 2	Day 1 (+3)	Day 7 (+3)	Day 14 (+3)	Day 30 (+10)	Day 60 (+10)	Day 90 (+10)	Day 180 (+20)		
	Clinic	Clinic	Phone	Phone	Phone	Phone	Phone	Phone	Phone	Phone	Phone	Phone
Informed Consent	X											
Inclusion/Exclusion Criteria	X											
Demographics	X											
Medical/CDI History	X											
Concomitant medications	X			X	X	X	X	X	X	X		
Randomization at University of Texas School of Public Health	X											
Pre-treatment preparation reminder (day -4 to -1) ¹	X											
Urine Pregnancy Test ²		X										
Confirmation of bowel prep and Imodium (groups 1-3) ³		X										
Vital signs ⁴ and Weight ⁵		X										
Stool Collection	X ⁶			X	X	X	X	X	X	X	X	
Study Drug Dose		X	X									
Diaries Distribution	X	X										
Diaries Receipt ⁷		X			X	X	X	X	X	X		X
AE Assessment/Monitoring for Safety		X	X	X	X	X	X	X	X	X	X	X

¹ Reminder can be via email or phone.

² Perform urine pregnancy test only on female subjects' of childbearing potential

³ If bowel prep is missed, subject can still proceed with FMT (noted as protocol deviation).

⁴ Vital signs before treatment, observe, and repeat vitals after at least 60 minutes

⁵ Weight measured before treatment only. Subjects will measure weight at home each Sunday morning before eating and record on diaries if they have a scale or balance.

⁶ Subject can collect stool any day after enrollment and before bowel prep on Day -1, and can bring stool sample on treatment day 1 clinic visit

⁷ Diaries can be submitted with stool samples or emailed, faxed or mailed (original can be provided later)

TABLE 2: SEVERITY GRADING

Parameter	Grade 1: Mild	Grade 2: Moderate	Grade 3: Severe	Grade 4: Potentially Life-threatening

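### The >5% weight-change criterion can be checked only in subjects who return home weights, but its percentage is taken over everyone dosed; the number actually weighed should be shown beside it

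*Combined protocol and SAP*

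**What the plan says.** Section 9.1.5 names weight gain in its heading as an adverse event of special interest. Its working criterion is a change in either direction: "subject-reported weekly weight data from diaries will be assessed for AE (>5% change from baseline weight) at days 60 and 180 phone visits".

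Where the weights come from:
- Footnote 5 to Table 1 limits study weighing to Day 1: "Weight measured before treatment only".
- After that, subjects are advised to weigh themselves at home each week and write the result in the diary, "providing they have a scale or balance" (9.1.5).
- Section 7.2 accepts gaps on both counts: "If they do not have the means to measure their weight this is not a protocol deviation", and "Diaries that are received out of the window or missed diaries are not a protocol deviation".

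How the event is summarised:
- Section 10.2.5 tabulates "The number and percentage of subjects reporting at least one occurrence of an adverse event and/or serious adverse event", by system organ class and preferred term. It names no denominator.
- Section 10.2.3 supplies one: "All analyses will be conducted using the intent-to-treat population", defined as every subject who began the procedure.
- No section defines a set of subjects evaluable for weight, or a rule for missing weights.

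Section 6 adds a route to missing data. Treatment failures have no further clinical follow-up, and those who are retreated leave the study after the second-day retreatment call.

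**The concern.** Any subject reached by telephone can report nausea or a fever, so an all-dosed denominator suits most adverse events. The weight criterion is different. It needs two measurements, and the plan makes the second one optional. A subject who never supplies it, and mentions no change by phone, is tabulated exactly like a subject who was weighed and stayed within 5%.

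Safety is a primary endpoint, and 10.2.3 compares it across the three doses and between groups 3 and 4. If the number weighed is not shown, a low weight-event percentage cannot be told apart from little weighing, and a difference between groups cannot be told apart from a difference in weighing. The gaps are not deviations either, so a deviation listing would not reveal them.

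**Working it through.** The plan states no weight-event rate, scale-ownership share or diary-return share, so there is no figure of its own to reproduce. Everything below marked as assumed is illustration.

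**Inputs**
- From 10.2.2: 90 subjects planned per group; assumed efficacy of 70%, 80%, 88% and 80% in groups 1, 2, 3 and 4.
- Assumed: r, the true share of subjects with a change above 5%; w, the share with usable follow-up weights; c, the share of events in unweighed subjects that still reach the table through a phone report.

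**1. Level of the rate.** If having weights is unrelated to weight change, and the weights are accurate,

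all-dosed percentage = r × [w + (1 − w) × c].

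With c = 1 this is r. With c = 0 it falls to r × w, so the relative shortfall is at most 1 − w. At c = 0:

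| Unweighed (1 − w) | True 10% reads | True 20% reads | True 30% reads |
|---|---|---|---|
| 10% | 9% | 18% | 27% |
| 20% | 8% | 16% | 24% |
| 30% | 7% | 14% | 21% |
| 40% | 6% | 12% | 18% |

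Under those two conditions these are floors. In a group of 90, 10% unweighed is 9 subjects.

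**2. No events seen.** The one-sided 95% upper bound is 1 − 0.05^(1/n). With n = 90 it is 3.3%. If only 72 (80%) were weighed it is 4.1%, and if only 54 (60%) were, 5.4%. Counting all 90 claims more reassurance than the measurements carry.

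**3. Comparison between groups.** With c = 0 and equal w, the risk ratio is unchanged and the risk difference shrinks by the factor w. With unequal w, a difference appears from nothing: a true 20% in both groups, with w = 0.8 and 0.6, reads 20% × 0.8 = 16% and 20% × 0.6 = 12%.

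**4. A route to unequal w.** The efficacy assumptions in 10.2.2 imply failures of 30%, 20%, 12% and 20% in groups 1 to 4. Suppose failures supply no weights after day 60, nothing else is missing, c = 0, and the true rate for days 61 to 180 is 20% in every group. The all-dosed percentages for that period are then:
- group 1: 20% × 0.70 = 14.0%
- group 2: 20% × 0.80 = 16.0%
- group 3: 20% × 0.88 = 17.6%
- group 4: 20% × 0.80 = 16.0%

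That is an apparent dose gradient produced by follow-up alone. It rests on reading diary weights as part of the follow-up that stops after failure, which the text does not settle for failures who are not retreated.

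**5. What a measured-subject denominator does.** Under the same independence assumption it returns r, but it does not recover information. Take an assumed 10% against 20%, compared by a two-sided 0.05 normal-approximation test with power Φ[(d − 1.96 × s0)/s1], where d is the difference and s0 and s1 are its pooled and unpooled standard errors. With 90 per group all weighed, power is 47%. At w = 0.6 it is 29% over all dosed (6% against 12%, n = 90) and 31% over those weighed (10% against 20%, n = 54).

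**The case against.** The strongest case against has five parts.

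- **The denominator is inferred.** Section 10.2.5 names none. This is true, but 10.2.3 applies its population to every analysis and nothing exempts this event.
- **Weight events can arrive by other routes.** Phone visits ask about new symptoms, worsening of baseline illness and metabolic syndrome (7.2, 8.5); 9.1.1 counts worsening according to the subject; 9.6 records spontaneous reports. This stands. A reader might infer that the event can be seen only in scale owners. The documents support less: diary weights are the only stated way to apply the 5% threshold, not the only way a weight event enters the table.
- **The reported rate may not end up too low.** The Day 1 weight follows a day of clear liquids in all groups and bowel preparation in groups 1 to 3 (8.1), and it is compared with weekly readings on home scales. Low baselines and scale differences can create false gains. This stands too. Missing weights push the rate down, but the net direction of all errors is not established.
- **Scale ownership precedes randomization**, so it should differ between groups only by chance. That is right for ownership. It does not cover diary return or the end of follow-up after failure.
- **The consequence is limited.** The safety analysis is descriptive, and the halting criteria in 9.10 do not use a weight rate. This bears on priority, not on whether the table can be read.

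It is also tempting to replace the all-dosed figure. That would go too far: events reported by phone in subjects without diary weights would drop out of the table.

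**Conclusion.** The point holds as a gap in how one special-interest event is summarised. Subjects with no follow-up weight are counted as free of the threshold event unless they report a change themselves, and nothing in the planned tables shows how many there are.

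If having weights is unrelated to weight change, the downward pull is at most the unweighed fraction in relative terms. Its actual size cannot be obtained from the documents, because both the event rates and the missing shares used here are assumptions. Distortion between groups is possible, not demonstrated; it needs weighing or follow-up to differ by group, and differing failure rates are one plausible cause. The change is worth making because it affects what can be concluded about weight by dose and bowel preparation, and it needs no new data.

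**What to change.** In 10.2.5, keep the all-dosed number and percentage in the adverse event table. For the >5% weight-change event, add a block per group and per period (to day 60; day 61 to 180) with:
- the number with a Day 1 weight and at least one diary weight in that period;
- the percentage of those with the event, gain and loss shown separately;
- the number with no weight data, stated to be missing and not event-free.

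The cost is one extra table block, with no new visit or measurement. Three limits should be stated with it. The measured-subject rate is unbiased only if having weights is unrelated to weight change. A subject weighed once early in a period counts as measured for all of it. And the block does not correct differences between the clinic scale and home scales.

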 - Remind subject to collect stool sample that will be placed in a transportation container with ice pack and delivered to the EPDL within 6 hours of collection if possible or as quickly as possible (excluding weekends and holidays) to be stored in the EPDL at -80° degrees for possible future testing. Remind subject to put stool collection date on provided container (if already submitted, stool collection date should be confirmed). Stool sample will not be collected for follow up visit Day 180. If hand delivery is not possible, stool sample may be shipped by Federal Express as expeditiously as possible. A FedEx shipping label, ice pack, Styrofoam container with shipping box and instructions will be provided to the subject to ship stool samples if they are not able to hand deliver to the EPDL. The EPDL will be closed on weekends and holidays. If follow-up day falls on Friday, Saturday or Sunday, subjects can collect and ship the sample on Thursday or the following Monday.
 - Remind subject to bring completed diaries with the stool sample, or fax, or email, or mail to the study site. For diary copies received in email or fax, an attempt will be made to obtain the originals from subjects to be taken to the study site subsequently. Diary will not be collected on follow up visit day 1 after treatment.
 - Assess subject for any adverse events, new illness symptoms, worsening of baseline illnesses including adverse events of special interest (new or worsening autoimmune conditions, and metabolic syndrome) and change in medication. Assess and review subject-reported weight data from diaries for AE (>5% change from baseline weight) at days 60 and 180 phone visits.

- Assess subject for solicited symptoms such as diarrhea (passage of ≥ 3 watery stools per 24-hour period for two consecutive days), nausea, vomiting, gas/flatulence, abdominal distension, abdominal cramps/pain, constipation, rectal bleeding, fatigue/malaise, chills/shivering and fever (> 99.9 F) up to 60 days after treatment.

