9. ASSESSMENT OF SAFETY AND EFFICACY

9.1 Assessment of Safety (Definition)

9.1.1 Adverse event:

Any untoward medical occurrence associated with the use of PRIM-DJ2727 whether or not considered drug related, and can therefore be

- Any symptom not previously reported by the subjects (medical history/pre-treatment diary). Wherever possible, a specific disease rather than individual associated signs and symptoms should be identified by the investigator. However, if an observed or reported sign or symptom is not considered a component of a specific disease by the investigator, it should be recorded as a separate adverse event.
- Clinical worsening of baseline parameters according to subject.
- A condition felt to be possibly related to treatment first detected or diagnosed after study drug administration

All adverse events (AEs) that occur within 180-200 days after treatment will be recorded as indicated above. Recurrence of CDI is not to be recorded as an adverse event unless hospitalization ≥ 24 hours is required for management, then recorded as serious adverse event.

9.1.2 Suspected adverse reaction:

Any adverse event for which there is a reasonable possibility that the study drug caused the adverse event. For the purposes of IND safety reporting, "reasonable possibility" means

there is evidence to suggest a causal relationship between the drug and the adverse event.

9.1.3 **Serious adverse event:**

Any adverse event or suspected adverse reaction is considered serious if in the view of the investigators it results in any of the following outcomes:

- Death
- Life-threatening adverse event
- Hospitalization \geq 24 hours
- Prolongation of existing hospitalization
- Substantial disruption of the ability to conduct normal life functions
- Congenital abnormally/birth defect
- Important medical events that jeopardize the patient, such as allergic bronchospasm requiring intensive treatment
- Persistent or significant incapacity or substantial disruption of the ability to conduct normal life functions

An emergency room visit without hospital admission will not be recorded as a serious adverse event (SAE) under this criterion, nor will hospitalization for a procedure scheduled or planned before signing of informed consent.

Death and life-threatening AEs possibly related to the study are reported by study coordinator or investigator within 24 hours to the IRB. Other SAEs potentially related to the study will be reported to the IRB within 7 days.

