9.3.2 Relationship

The relationship of an adverse event to FMT will be assigned by the Investigator according to the following definitions:

- *Probable*: a reaction that follows a reasonable temporal sequence from the procedure that follows a known or expected response pattern to the suspected procedure and that could not be reasonably explained by the known characteristics of that subject's clinical state
- *Possible*: a reaction that follows a reasonable temporal sequence from the procedure that follows a known or expected response pattern to the procedure but could readily have been produced by a number of other factors

- *Unlikely*: a reaction that does not follow a reasonable temporal sequence from the procedure but for which causality from FMT cannot be ruled out.
- *Not related*: a reaction for which sufficient data exist to indicate that the etiology is unrelated to the procedure

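### The safety tables use no onset window, so adverse events up to Day 180-200 dilute any early difference caused by a two-day capsule course or one evening of bowel prep

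*Combined protocol and SAP*

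**What the plan says.** Section 10.2.5 is the whole safety analysis. Its main summary is "The number and percentage of subjects reporting at least one occurrence of an adverse event and/or serious adverse event", given "for each system organ class and preferred term will be tabulated". For repeats of one event, "the adverse event with the highest severity will be tabulated", and the event counts as related if any occurrence was related. The section adds "Term will also be tabulated by severity and by the relationship to the procedure" and "All adverse events and or serious adverse events for all subjects will be presented in data listings", with narratives for serious events. It names no onset window, no event counts and no between-group estimate.

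Section 9.1.1 sets the period: "All adverse events (AEs) that occur within 180-200 days after treatment will be recorded as indicated above". Section 8.5 stops the named-symptom checklist earlier, asking about symptoms such as "fatigue/malaise, chills/shivering and fever (> 99.9 F) up to 60 days after treatment".

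Safety by dose, and safety without bowel prep and Imodium, are primary endpoints (Synopsis, Sections 2 and 9.11). Section 10.2.3 makes them two primary analyses: groups 1-3 by dose, and group 3 versus group 4. Under Section 8.1 the exposures are capsules on two consecutive days and, in groups 1-3, bowel prep on the evening of Day -1 and one loperamide dose on Day 1.

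**The concern.** Direct tolerability effects of so short an exposure should fall mainly in the first days. An ever/never percentage over about six months adds every later event of the same term or organ class to that early signal. A subject with background nausea on Day 120 counts the same as one with nausea on Day 2. If later events are equally common in all arms, they leave less room for an early difference to show, and the observed difference shrinks.

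The way events are found also changes part-way. The named symptoms are asked about one by one to Day 60. After that, only general adverse-event questions remain. One percentage therefore mixes two ascertainment methods.

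At stake is the sensitivity of the table that carries a primary endpoint. A small whole-period difference could be taken as similar tolerability when the early difference was larger.

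**Working it through.** **Inputs from the documents.** 90 per group (Section 10.2.2). Recording for 180-200 days (Section 9.1.1), taken as 190. Checklist to Day 60 (Section 8.5). Follow-up calls on Days 1, 7, 14, 30, 60, 90 and 180 (Table 1). The plan states no power or event rate for safety, so there is no figure to reproduce.

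**Assumptions.** Acute risks e of 10% and 25% in the two groups, all with onset by Day 14. A background risk b over 190 days that is equal in both groups, independent of the acute event, and constant over time. Two-sided test at 0.05, used only as a yardstick.

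**Formulas.**
- Whole-period risk: q = 1 - (1 - e)(1 - b), so the difference is (e2 - e1)(1 - b).
- Background within the first 14 days: b14 = 1 - (1 - b)^(14/190).
- Power = Φ[(d - 1.96·SE0)/SE1], where d is the difference, SE0 = √(2p̄(1 - p̄)/90), p̄ is the mean of q1 and q2, and SE1 = √([q1(1 - q1) + q2(1 - q2)]/90).

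**Worked cases.**
- No background: SE0 = 0.0566 and SE1 = 0.0555. (0.15 - 0.1110)/0.0555 = 0.70, so power is 0.76.
- Background 20%, whole period: q = 28% and 40%, SE0 = 0.0706, SE1 = 0.0700. (0.12 - 0.1384)/0.0700 = -0.26, so power is 0.40.
- Background 20%, Days 1-14: b14 = 1.6%, q = 11.5% and 26.2%, difference 14.8 points, power 0.72.

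| Background over 190 days | Whole-period rates | Difference (points) | Power, whole period | Power, Days 1-14 |
|---|---|---|---|---|
| 0% | 10.0% vs 25.0% | 15.0 | 0.76 | 0.76 |
| 2% | 11.8% vs 26.5% | 14.7 | 0.71 | 0.76 |
| 5% | 14.5% vs 28.8% | 14.3 | 0.64 | 0.75 |
| 10% | 19.0% vs 32.5% | 13.5 | 0.54 | 0.74 |
| 20% | 28.0% vs 40.0% | 12.0 | 0.40 | 0.72 |
| 40% | 46.0% vs 55.0% | 9.0 | 0.23 | 0.67 |

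The 40% whole-period entry counts both rejection tails (0.226); the upper tail alone gives 0.225.

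**Other assumed rates show the same pattern.** With 15% versus 35%, power is 0.88 without background. Over the whole period it is 0.81, 0.59 and 0.28 at backgrounds of 5%, 20% and 50%. Within Days 1-14 it is 0.87, 0.86 and 0.81. With three dose groups at 15%, 25% and 35% (2 degrees of freedom), whole-period power is 0.80 with no background, 0.49 at 20% and 0.22 at 50%.

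**The case against.** The strongest reply is that the plan already limits dilution.
- It tabulates preferred terms as well as organ classes, and a single term can have a low background. At 2% to 10% the table above shows power of 0.71 to 0.54, a mild to moderate loss.
- Symptoms reported before treatment and unchanged are not adverse events (Sections 9.1.1, 9.4 and 9.5). Baseline comes from a two-week history and a daily diary, so a 40% background for one symptom is hard to assume.
- The relationship table uses timing. Section 9.3.2 describes an unlikely relationship as "a reaction that does not follow a reasonable temporal sequence from the procedure", so late unrelated illness should stay out of the related columns.
- No between-group test of adverse events is planned, so the power figures measure lost sensitivity and not the failure of a planned test.

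All of this stands and limits the size of the point. It does not remove it. Relationship is an investigator's judgement and group 4 is unblinded, so that table cannot replace a time window. Listings are not a comparison.

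Three stronger readings are tempting, and the documents do not support them.
- A reader might infer that early effects are swamped, or that every arm nears saturation. That needs a high background rate, and the documents give none.
- A reader might infer that events after Day 60 come only from spontaneous reports. Sections 7.2, 8.5 and 9.6 require adverse-event questions at every contact, and Table 1 marks the assessment on Days 90 and 180. Only the named checklist stops.
- A reader might infer that a severe unrelated episode on Day 150 erases a mild related one on Day 2. The severity rule covers only repeats of the same event, and the term stays counted as related. Only the severity row changes.

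**Conclusion.** The point holds as a moderate weakness in how a primary endpoint is summarised. With no onset window, events up to Day 180-200 dilute early differences in both primary safety comparisons. The loss is slight for low-background preferred terms and substantial for broad organ-class counts: under the assumed 10% versus 25%, power falls from 0.76 to 0.64 at 5% background and to 0.23 at 40%. These sizes rest on assumed acute and background rates, equal and independent background, constant hazard, and acute effects that end by Day 14.

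A reader might also infer that a window would fully repair group 3 versus group 4. It would not. Section 9.5 says that mild to moderate diarrhea from the prep and mild constipation from Imodium in groups 1-3 are not to be recorded as adverse events. Those effects are absent from the data rather than diluted, and no onset window can recover them.

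**What to change.** In Section 10.2.5, pre-specify adverse-event tables by group and onset window, for example dosing to Day 14, Day 15-60 and after Day 60. Day 60 matches the end of the checklist. Assign events by onset date, not call date, because the calls have windows of their own. Apply the highest-severity and relatedness rules within each window. For the early window, report between-group risk differences with confidence intervals, for groups 1-3 and for group 3 versus group 4. Keep the whole-period table, as the main one for serious and special-interest events.

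The cost is SAP wording and extra table columns. Section 9.2 already has event dates recorded, and early calls exist, so no new data are needed. There is a small downside: the cut points are a judgement and each window holds fewer events. Fix the cuts before outcome data are seen, so that they cannot look data-driven.

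Separately, reconcile the recording exclusion in Section 9.5 with the group 3 versus group 4 safety comparison in Section 10.2.3.
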